8.3.4 Serious Adverse Events (SAEs)

All SAEs as defined below and that occur after the first dose of camostat mesilate and up to Day 28 must be reported to the Sponsor as soon as the site becomes aware of them. Any SAEs occurring after Day 28 and considered at least possibly drug-related must also be reported.

8.3.5 Definition of Serious Adverse Events

An SAE is an AE from this study that results in any of the following outcomes:

- Death (even if caused by COVID-19 all deaths are recorded as SAEs)
- Life-threatening situation (subject is at immediate risk of death)
- Inpatient hospitalization or prolongation of existing hospitalization
- Persistent or significant disability/incapacity
- Congenital anomaly/birth defect in the offspring of a subject who received study drug

NOTE: Important medical events that may not result in death, be immediately life-threatening, or require hospitalization, may be considered an SAE when, based upon appropriate medical judgment, they may jeopardize the subject *and* may require medical or surgical intervention to prevent one of the outcomes listed in this definition.

A life-threatening AE is defined as any adverse experience that places the subject in the view of the Investigator, at immediate risk of death from the event as it occurred. This does not include an event that might have led to death, if it had occurred with greater severity.

"Inpatient hospitalization" means the subject has been formally admitted to a hospital for medical reasons, for any length of time with a minimum one overnight stay. Presentation and care within an emergency department does not necessarily constitute an SAE. Complications that occur during hospitalization are AEs. If a complication prolongs hospitalization, it is an SAE.

8.3.6 SAE Reporting Requirements to the Sponsor

The procedure for reporting SAEs, regardless of causal relationship, is as follows:

- Within 24 hours of the Investigator's knowledge of an SAE, the site must notify the Sponsor by phone call to their site monitor, medical monitor or other Sponsor representative. They should also immediately complete the AE eCRF and select "Serious".
- This initial reporting of an SAE should contain as much information as is available to the Investigator. Submission of the SAE via the EDC should not be delayed in order to collect additional information to complete the form.
- Follow-up SAE reports may be generated in cases in which additional information becomes available. Hospital records, autopsy reports, and other documents may become available and scanned copies can be provided to the Sponsor when applicable. The follow-up SAE report should describe whether the event has resolved or continues, if and how it was treated, whether

Confidential Page 28 of 42

the blind was broken or not, and whether the subject continued or withdrew from study participation.

- The Sponsor will distribute completed SAE forms, which may be used to notify the IRB when applicable, via a secure internet-based document depository.
- The Investigator should notify the IRB of Serious Adverse Events occurring at the site and other adverse reports received from the Sponsor in accordance with local procedures.

The Investigator must take all therapeutic measures necessary for resolution of the SAE. Any medications necessary for treatment of the SAE must be recorded onto the concomitant medication section of the subject's eCRF. However, treatment medication should only be recorded in the narrative description section of the SAE form.

8.4 Suspected Unexpected Serious Adverse Reactions (SUSARs)

A SUSAR carries specific and time-based reporting requirements for the Sponsor of a clinical trial. Thus, after an Investigator reports an SAE, the FDA expects the Sponsor will determine whether it meets the definition of a SUSAR.

A SUSAR is defined according to 3 criteria:

- 1. The AE is deemed a "suspected adverse reaction" if there is a reasonable possibility that the study drug caused the AE. A "reasonable possibility" means there is evidence to suggest a causal relationship between the drug and adverse event.
- 2. The AE is "Serious" if it meets the definition of an SAE provided in section 8.3.5
- 3. The AE is deemed "unexpected" if it is not listed in the Investigator's Brochure (IB) or if in the IB, has not been reported at the severity observed.

In cases where the Sponsor deems a SUSAR has occurred, it must file an IND Safety Report with the FDA. Sponsorwill require the assistance and cooperation of the Investigator and staff to provide accurate and complete information on the subject and observed SAE so that reporting requirements to the FDA can be met.

8.4.1 Reporting SUSARs to the FDA: IND Safety Reports

IND safety reports are used to submit reports of SUSARs to the FDA. There are 2 types of reports:

- A "15-day report" is used when the reported SAE is a SUSAR and requires that as much information as is available to the investigator and the sponsor, be submitted to the FDA in on the appropriate form. For US trials, the appropriate form is the FDA Form 3500A also commonly known as a "MedWatch" form.
- A "7-day report" is used when the SUSAR is considered to be fatal or life-threatening.

The 7-day and 15-day timelines begin the day that the Investigator learns of the event and are counted in calendar days – not business days. Therefore, it is important that the investigator carefully follow the reporting requirements described in section 8.3.6.

8.5 Clinical Laboratory Abnormalities and Other Abnormal Assessments

Laboratory abnormalities are usually not recorded as AEs unless considered to be clinically significant by the site clinician. An abnormal laboratory result will be considered an AE if it

Confidential Page 29 of 42

induces clinical signs or symptoms, if the abnormality is of a degree that requires active management (e.g. discontinuation of the study drug, dose modification) or when the event is requiring treatment or other therapeutic intervention (e.g. iron supplements, blood transfusion, etc.).

The Investigator will evaluate the relationship of any significantly abnormal result to protocol treatment and clinical condition, if possible. All clinically significant abnormal laboratory results will be followed until they return to normal or become stabilized.

8.6 Handling of Overdose

An overdose is defined as any dose greater than the highest daily dose included in this document. Any overdose must be recorded. If the overdose is associated with an AE, that AE must be recorded, assessed for seriousness, and reported as an SAE.

9 STATISTICAL METHODS

Complete details of all statistical analyses, including methods for handling missing data, will be included in a formal statistical analysis plan (SAP), to be completed as soon as possible.

9.1 General Considerations

For the primary comparison, the following will be tested:

- Null hypothesis: AUC of viral shedding through day 10 is equal in control and treatment;
- Alternative hypothesis: AUC of viral shedding through day 10 differs between control and treatment.

Hypothesis tests will be two sided and conducted at an overall alpha = 0.05 level of significance.

The number of hospitalizations and emergency department visits will be estimated for each arm, with 95% confidence intervals. The frequency of adverse events and serious adverse events will be tabulated by type and by treatment arm. AEs will be compared by arm using the Chi-squared test or Fisher's exact test, as appropriate, in the safety analysis set.

9.2 Sample size justification

Approximately 120 patients will be enrolled.

Assuming 1:1 randomization and the use of a two-sided log rank test at the alpha=0.04999 level of significance for the final analysis, 120 patients (60 per arm) events will provide 80% power to detect an effect size of 0.5 using two-sample t-test. This leaves alpha=0.00001 to check for overwhelming efficacy after 50% of participants have completed 24 hours of follow-up.

9.3 Demographic and Baseline Characteristics

Summary statistics will be provided per treatment group for demographic (e.g., age, height, weight, body mass index [BMI], race, gender) and other initial subject characteristics (e.g., medical history,

Confidential Page 30 of 42

concomitant diseases) will be provided per treatment group and for the total group. The ITT population will be used for the summaries.

9.4 Analysis Populations

The following analysis populations will be defined for the study:

The intent-to-treat (ITT) population will include all randomized patients. Patients will be analyzed according to their assigned treatment arm. All efficacy analyses will be completed in the ITT population.

The safety population will include all patients who receive study treatment. Patients will be analyzed according to actual treatment received. All safety analyses will be completed in the safety population.

9.5 Stratification, Subgroup Analysis and Pooled Analysis

Following consent, those subjects meeting all entry criteria will be randomized in a 1:1 ratio

Treatment Arm: camostat mesilate + SOC

Control Arm: placebo + SOC

Randomization will be stratified by age (>=50 and <50 years old) and sex.

Members of the same household may participate in the study as long as the inclusion and exclusion criteria are met. Because this is a double-blind, placebo-controlled trial, subjects from the same household will be randomized just as any other subject.

9.6 Efficacy Endpoint Analysis

9.7 Descriptive analyses

Descriptive statistics (proportions for categorical variables, means, medians, standard deviations and interquartile ranges for continuous variables) will be reported for all key patient variables, including baseline and demographic characteristics, use of medications, compliance, and study completion status. Data that are missing on key patient characteristics and the outcome will be fully described, including any patterns of missingness (i.e., any relationships between missingness of a variable and patient characteristics).

A CONSORT diagram displaying the number of patients screened, eligible, and consented along with reasons for ineligibility will be provided. Graphical tools such as histograms, boxplots, and scatterplots will be created to assess quality of data and to display patterns over time.

9.8 Primary efficacy analysis

To address our primary objective, the AUC SARS-CoV2 viral RNA levels during follow-up will be estimated using the linear trapezoidal method, and mean AUC levels compared between groups using a linear regression model regressing log(AUC) on treatment arm, site, age, and sex. If more than 3 sites are included to address the objectives, we will employ a mixed effects

Confidential Page 31 of 42

model, with a random effect for site. The test will be performed at the two-sided alpha = 0.05 level of significance.

9.9 Secondary efficacy analyses

Time until shedding cessation will be compared between the two treatment arms using a Cox proportional hazards model adjusted for site, age, and sex. Time of cessation will be defined as the first negative result that is followed only by negative results. If more than 3 sites are included to address the objectives, we will employ a stratified Cox model, stratified by site, allowing each site to have its own baseline hazard. The hazard ratio for shedding cessation will be estimated, along with its 95% confidence interval, from a Cox proportional hazards model. If the proportional hazards assumption is not met, we will consider an extended Cox model that relaxes the proportional hazards assumption

The distribution of shedding cessation will be estimated using the Kaplan-Meier method, and Kaplan-Meier curves will be presented for each treatment arm. Time to shedding cessation at the end of the study period along with 95% confidence intervals will be presented for each treatment arm.

The distribution of time to resolution of symptoms will be estimated using the Kaplan-Meier method, and Kaplan-Meier curves will be presented for each treatment arm. Time to resolution of symptoms at the end of the study period along with 95% confidence intervals will be presented for each treatment arm. The hazard ratio for resolution of symptoms will be estimated, along with its 95% confidence intervals, from a Cox proportional hazards model. Time to resolution of symptoms will be determined by analysis of daily questionnaires (see Appendix A2). Resolution of symptoms requires that symptoms are mild or absent for at least 24 hours. The analysis of symptom resolution will be conducted on the symptomatic ITT population, i.e. participants who report moderate or severe symptoms at baseline. These analyses will be repeated in a second analysis considering only respiratory symptoms, i.e. fever, cough, shortness of breath, sore throat, headache, and nasal congestion/runny nose. This analysis will be performed on the subset of patients who report moderate or severe respiratory symptoms at baseline.

The number of hospitalizations, emergency department visits, incidence of respiratory failure, deaths, and proportions of subjects alive, not hospitalized, and free of respiratory failure will be estimated for each arm, with 95% confidence intervals. Respiratory failure is defined as the need for mechanical ventilation, ECMO, non-invasive ventilation, or high-flow oxygen

Our analyses will use multiple imputation methods that assume data are missing at random by including all baseline characteristics, treatment assignment, and reasons for missingness in the imputation model. This approach will be applied to any analysis involving endpoints or key variables where any missing data occurs in order to adhere to the ITT principle. Assumptions regarding missingness will be addressed in sensitivity analyses.

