|---------------------------|---|--|--|--|
| | Secondary Endpoints | | | |
| | AUC of shedding of SARS-CoV-2 virus calculated using the RT-PCR measures of viral load from self-collected nasal swabs on days 1-10, 14, 21, and 28. Time until cessation of shedding of SARS-CoV-2 virus, defined as the time in days from randomization to the first negative RT-PCR result of self-collected nasal swabs that is followed by only negative results (i.e. no later positive results are observed). RT-PCR results from oropharyngeal swabs collected on Days 1, 5, 10 and 28 Clinical worsening of COVID-19 in symptomatic subjects (clinical worsening defined the development of respiratory distress or symptoms that require hospitalization) Adverse events AEs and clinical laboratory tests for systemic safety including hematology and clinical chemistry Mortality Development of antibodies to SARS-CoV-2 Time until resolution of symptoms (resolution of symptoms defined as absence of moderate or severe symptoms for at least 24 hours for those reporting moderate or severe symptoms at baseline). | | | |
| | 9. Drug level on day five, one hour after a dose taken on an empty stomach. | | | |
| Study Sites | Stanford University School of Medicine | | | |
| Planned Enrollment | 120 (60 in the camostat mesilate + SOC group and 60 in the placebo + SOC group) | | | |
| Study Population | Adults with confirmed SARS-CoV-2 who are experiencing mild-moderate symptoms | | | |
| Subject Entry Criteria | Inclusion Criteria (all questions must be answered YES) 1. Adults (18-80) 2. Diagnosis of COVID-19 disease: a. Presence of mild-moderate symptoms without signs of respiratory distress (as defined by SpO2 <=94% on room air, RR >=24, HR >=110), with FDA-cleared molecular diagnostic assay positive for SARS-CoV-2 within 72 hours from initial swab to the time of commencing informed consent: Disease is defined as having at least 2 of the following symptoms that are of moderate or higher severity as scored on the COVID Outpatient Symptom Scale (COSS): i. Fever (>98.7F) | | | |

Confidential Page 7 of 42

| • • | \sim 1 |
|-----|----------|
| 11. | Cough |
| | Cousii |

- iii. Shortness of breath
- iv. Fatigue
- v. Headache
- vi. Body ache
- vii. Joint pain
- viii. Chest pressure
- ix. Abdominal pain
- x. Sore throat
- xi. Nasal congestion
- xii. Chills
- xiii. Feeling hot or feverish
- xiv. Runny nose
- xv. Loss of taste
- xvi. Loss of smell
- xvii. Diarrhea
- xviii. Nausea
- xix. Vomiting
- xx. Rash

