- c. If she is of childbearing potential will strictly adhere to the following contraceptive measures during the study and for seven days following the last dose of study medication:
 - i. Abstain from sexual intercourse, OR,
 - ii. Must ensure that her male partner agrees to use a condom during sexual intercourse and agree to use an approved method of contraception (e.g., IUD, diaphragm with spermicide, oral contraceptives, injectable progesterone, or subdermal implants).
- d. Agrees to stop breast-feeding prior to first dose of study drug and through seven days after completing therapy.
- e. Has a negative urine pregnancy test at screening.
- f. Has not had unprotected sexual intercourse within the past month.
- 6. When such testing is available, subject will be confirmed to be SARS-CoV2 infected using a rapid (<30 minute) SARS-CoV2 point-of-care test; if such a test is not available, this step of screening will be omitted.
- 7. Subject agrees to maintain home or other quarantine as recommended by the study physician, except to visit the study site as required by the protocol.
- 8. Subject agrees to take daily nasal swabs (anterior nares) for Day 1 to Day 10 and Day 14, 21, and 28 using the study provided material and bring these to their follow up visits on days 5, 10 and 28.
- 9. Subject agrees to record daily symptoms, temperature, oxygen saturation, and pulse using the study provided materials.
- 10. Subject agrees to return to the study site for follow-up visits on Day 5, 10 and 28. The study site will be staffed by trained healthcare providers wearing full personal protective equipment and study site equipment will be disinfected between patients according to the same protocols as a clinical setting. Subjects will be wearing masks, will be appropriately spaced, and the number of subjects assessed at each time will be limited.
- 11. Members of the same household may participate in the study as long as the inclusion and exclusion criteria are met.

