7.1 Day 1 (PRE-DOSE)

- Obtain informed consent.
- Verify eligibility per the inclusion and exclusion criteria. (See Sections 5.1 and 5.2)
 - o Review and record medical history to ensure there are no exclusionary illnesses.
 - Review and record concomitant medications for possible prohibited medications. (See Section 6.7)
 - Record date of onset of symptoms
- If subject is female of child-bearing potential and meets inclusion criteria 5.e, obtain urine pregnancy test and proceed if result is negative.
- Measure and record vital signs (BP, HR, Temp, Resp).

Confidential Page 23 of 42

² If such symptoms are observed, administration should be discontinued.

- Collect and record SPO2 by Finger Sensor
- Perform Physical exam (may be done by the Principal Investigator or their designee)
- Collect oropharyngeal swab for virologic testing by RT-PCR and resistance testing.
- Collect blood samples for:
 - o Antibodies to SARS-CoV-2.
 - o Hematology and clinical chemistry laboratory analyses
 - Biobanking
- Perform subject randomization (via EDC) to establish treatment arm (camostat mesilate + SOC or SOC + placebo).
- Explain in home procedures for the study (self-sampling of nasal swabs, temperature, SPO2, completing the daily questionnaire).
- Provide supplies to research subject and review the calendar of return visits

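### Patients whose nasal swabs are PCR-negative on Day 1 and at every later visit count as shedding-cessation events at about time zero, which dilutes the hazard ratio

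*Combined protocol and SAP*

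**What the plan says.** The synopsis times the endpoint as "the time in days from randomization to the first negative RT-PCR result of self-collected nasal swabs that is followed by only negative results", and section 9.9 repeats the event rule: "Time of cessation will be defined as the first negative result that is followed only by negative results". The comparison is specified as follows: "Time until shedding cessation will be compared between the two treatment arms using a Cox proportional hazards model adjusted for site, age, and sex". On the population, section 9.4 says "All efficacy analyses will be completed in the ITT population", and that population is everyone randomised. Sections 8.1 and 14 schedule nasal swabs on Days 1 to 10, 14, 21 and 28.

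Entry (section 5.1, item 2) rests on a positive molecular assay from a swab taken up to 72 hours before consent. The specimen type is not named. The date of symptom onset is recorded, but no maximum duration is set. Item 6 adds a rapid confirmatory test, but "if such a test is not available, this step of screening will be omitted".

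For the symptom endpoint the same section does set a baseline condition: "The analysis of symptom resolution will be conducted on the symptomatic ITT population", meaning those with moderate or severe symptoms at baseline. No matching condition is given for shedding.

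The pre-dose list in section 7.1 includes an oropharyngeal swab. For nasal swabs it has only this instruction: "Explain in home procedures for the study (self-sampling of nasal swabs, temperature, SPO2, completing the daily questionnaire". Section 7.2 then gives the first dose. Section 14 shows a nasal swab on Day 1 without placing it before or after that dose.

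**The concern.** A patient cannot stop shedding in the nose if the nasal swab was already negative at the start and stayed negative. Under the event rule and the ITT rule together, such a patient is a success on Day 1, before treatment can act, and is equally likely to be in either arm. The Cox estimate then mixes the effect in shedders with a block of tied null events, and the Kaplan-Meier curves of both arms drop together at the origin. The same patients count as negative on Days 7, 14 and 28 for secondary objective 4.

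Section 2.7 says the trial will assess the time course of shedding cessation and is expected to support a larger study. A diluted hazard ratio could understate the effect passed on to that study. The plan's silence carries a second risk: some survival software drops records with zero follow-up time. The patients could then leave the analysis by default rather than by a planned rule.

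**Working it through.** **Design figure.** The plan gives no hazard ratio, event count or power for shedding cessation. Its only design figure (section 9.2) is 80% power for 60 per arm at a standardised effect of 0.5 and alpha 0.04999. The normal approximation gives Φ(0.5 × √(60/2) − 1.96) = Φ(0.78) = 78.2%, and the t-test gives 77.5%. That figure concerns a comparison of means and says nothing about this endpoint.

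**Inputs from the documents.** 60 per arm, 1:1 allocation, the swab days above, and a two-sided test at 0.05.

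**Assumed inputs.** The share q persistently negative from Day 1, the true hazard ratio in shedders (above 1 means faster cessation on camostat) and the control median.

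**Simulation A.** Exponential cessation times, control median 9 days, true HR 1.75, Cox model with treatment only, Efron ties, 1,500 replicates per cell. Each cell shows mean HR, then power.

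| q | negatives kept as time-zero events | negatives excluded |
|---|---|---|
| 5% | 1.69, 79% | 1.74, 82% |
| 10% | 1.64, 73% | 1.76, 80% |
| 20% | 1.55, 63% | 1.75, 74% |
| 30% | 1.46, 50% | 1.74, 67% |

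With a true HR of 1.0 the mean estimate stays between 0.99 and 1.01 and the rejection rate is about 5%. With a true HR of 1.5 and q = 20%, the estimate is 1.37 with 38% power when kept, against 1.49 and 45% when excluded.

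**Hand check of A.** Time-zero events split evenly between arms contribute a log HR of zero, so the pooled log HR is roughly (1 − share of events at time zero) × log HR. The last swab is 27 days after Day 1, so 2^(−27/9) = 12.5% of control shedders and 2^(−1.75 × 27/9) = 2.6% of treated shedders are censored. The average is 7.6%, so 92.4% have events. At q = 20% the time-zero share of events is 0.20 / (0.20 + 0.80 × 0.924) = 0.213, and 1.75^(1 − 0.213) = 1.55, as simulated.

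**Simulation B.** Weibull times (shape 1.5), control median 10 days, true HR 1.8, Efron ties. Ranges cover repeated runs, and Monte Carlo error on power is about 1.5 points at 800 runs.

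| q, all persistent | kept | restricted to Day 1 positives |
|---|---|---|
| 5% | HR 1.71 to 1.72 | 1.77 |
| 10% | 1.64 to 1.67, 75% | 1.75 to 1.77, 80 to 82% |
| 20% | 1.55 to 1.56, 63 to 66% | 1.74 to 1.76, 74 to 77% |

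**When some Day 1 negatives later test positive.** Same settings as B. The others are assumed to have the same cessation distribution as shedders, and the restricted analysis drops every Day 1 negative.

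| Day 1 negative | of whom persistent | all randomised | restricted |
|---|---|---|---|
| 10% | half | 1.69, 80% | 1.74, 81% |
| 20% | half | 1.66, 78% | 1.77, 77% |
| 20% | a quarter | 1.72, 83% | 1.78, 77 to 79% |

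The restriction still removes the dilution, but power is unchanged in the first two rows and lower in the third.

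**The case against.** Entrants had a recent positive assay, at least two symptoms of moderate or higher severity and, where available, a rapid confirmation. The persistently negative share may therefore be small. At 5% the shift from 1.77 to 1.71 is ln(1.77/1.71) = 0.034 on the log scale, against a standard error near 0.19. The dilution is conservative, the endpoint is secondary and unpowered, and all-randomised is the declared population. Section 9 also defers full analysis details to a formal SAP. All of this stands. It limits the size and urgency of the point but does not supply the missing rule.

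The documents do not support three stronger readings:

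- A reader might infer that every Day 1 negative is scored at time zero. The rule requires that no later swab be positive, so a Day 1 negative with one later positive gets a later event time and remains informative.
- A reader might infer from section 7.1 that the first nasal swab is taken after the first clinic dose. Sections 7.1, 7.2 and 14 leave the order open. Self-sampling is explained and supplies are handed over before dosing.
- A reader might infer that the ITT proportions for objective 4 are wrong. They are a valid comparison of all randomised patients and simply answer a different question.

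Restricting the set does not break the randomised comparison if membership is fixed by a pre-dose value.

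**Conclusion.** The point holds for patients negative on Day 1 and on every later nasal swab. Time-zero scoring follows from the event definition combined with the ITT rule; the plan neither states it nor rules it out. The result is dilution of any true effect, with no inflation of type I error.

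For an assumed true HR of about 1.8, the bias is minor at 5% persistently negative and material from about 10 to 20%. These sizes rest on the assumed share, hazard ratio and control median, none of which the documents give. The case for the restriction is that its estimate refers to patients who were shedding. A power gain is not guaranteed.

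**What to change.** In section 9.9 and the synopsis, define the set for time to shedding cessation (Cox and Kaplan-Meier) as randomised patients whose pre-dose Day 1 nasal swab is PCR-positive, parallel to the existing symptom rule. Report the full ITT result alongside as a sensitivity analysis, stating how persistently negative patients are scored. Report the Day 7, 14 and 28 negative proportions in the same set as a supplement to ITT.

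In section 7.1, state that the participant self-collects the Day 1 nasal swab before the first dose, so that the set is defined before treatment.

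The cost is a sentence in each of two places and one line in section 7.1. No swab is added, because the Day 1 swab is already scheduled. The downside is that Day 1 negatives who later test positive also leave this secondary analysis, with a small loss of information. The change should be made before unblinding.

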15 APPENDIX

Appendix A: Subject Status

1. ECOG Performance Status

GRADE ECOG PERFORMANCE STATUS

- Fully active, able to carry on all pre-disease performance without restriction
- Restricted in physically strenuous activity but ambulatory and able to carry out work of light or sedentary nature, e.g., light housework, office work
- Ambulatory and capable of all selfcare but unable to carry out any work activities; up an about more than 50% of waking hours
- 3 Capable of only limited selfcare; confined to bed or chair more than 50% of waking hour
- 4 Completely disabled; cannot carry on any selfcare; totally confined to bed or chair
- 5 Dead

2. Study Specific Daily Symptom Status Questionnaire

COVID-19 Outpatient Symptom Scale (COSS):

The below is a copy of a sample self-assessment a participant will be required to assess:

| | Oral temperature. | F | | |
|---|--|-------|------|--|
| | Time temperature was obtained. | A | M/PM | |
| Please take your oral temperature and assess your oxygen saturation with your pulse oximeter. | Blood oxygen saturation. | % | | |
| | Did you take a nasal swab today (study day 1-10,14,21,28)? | Yes / | No | |
| | Have you taken your study drug as prescribed in the last 24 hours? (study day 1-10) | Yes / | No | |
| | If it is written on your schedule (clinic visit day 3, 14, 28): did you collect your stool sample for your next visit? | Yes / | No | |

daily.

COVID-19 Outcome Symptom Scale (COSS) Daily Questionnaire

The following questions are about how you feel and how things have been during the past 24 hours compared to your typical health. Give the one answer that comes closest to the way you have been feeling. Select "None" if you have not had this symptom.

| Cough? | | | | | | | |
|---|------|--|------------------------------------|--|--|--|---------------------------------|
| | None | | Mild; just a few coughs per day | | Moderate; frequent but I can tolerate it | | Severe; I am very uncomfortable |
| Shortness of breath (difficulty breathing)? | | | | | | | |

Confidential Page 39 of 42

| | None | | Mild; just short of breath with exercise | | Moderate; I get short of breath doing daily activities | ☐ Severe; I feel I can't get enough air even at rest | | |
|-----------------------|--|-------|---|--|--|---|---|--|
| Fatigue (low energy)? | | | | | | | | |

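### A single good diary day counts as symptom resolution, and diary days lost to hospitalisation or death fall to missing-at-random imputation, so the symptom hazard ratio can be distorted

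*Combined protocol and SAP*

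**What the plan says.** Synopsis secondary endpoint 8 is time until resolution, with "resolution of symptoms defined as absence of moderate or severe symptoms for at least 24 hours". Section 9.9 repeats the rule ("Resolution of symptoms requires that symptoms are mild or absent for at least 24 hours") and takes the data from the daily COSS questionnaire in Appendix A2. That questionnaire asks about "how you feel and how things have been during the past 24 hours".

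For the effect measure, section 9.9 says "The hazard ratio for resolution of symptoms will be estimated, along with its 95% confidence intervals, from a Cox proportional hazards model". The analysis is repeated for respiratory symptoms. The synopsis statistics mention only the median per arm.

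In the same section, viral shedding has a durability condition: "Time of cessation will be defined as the first negative result that is followed only by negative results". Symptoms have none.

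For this endpoint the plan does not say how hospitalisation or death is handled. Section 9.9 estimates hospitalisations, respiratory failure and deaths separately. Its general missing-data rule is multiple imputation assuming missing at random: "This approach will be applied to any analysis involving endpoints or key variables where any missing data occurs". Sensitivity analyses on missingness are promised but not described.

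**The concern.** Secondary objective 3 concerns the duration of symptoms. Because one entry covers 24 hours, a single entry without a moderate or severe symptom satisfies the definition. The event is then the first good day, and a patient who is ill again the next day has already been counted as resolved.

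Diary days that go missing after admission or death have no rule of their own, so the general imputation rule applies. Read literally, it can impute good days, and hence a recovery, for a patient who has died. Including reasons for missingness in the imputation model does not cure this, because no patient has an observed diary after death from which the model could learn.

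At stake is a clinical-benefit hazard ratio, used twice in section 9.9, in a trial that section 2.7 says is expected to support a larger pivotal study.

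**Working it through.** **The plan's own figures.** The documents give no hazard ratio, event count, recovery rate or power for symptom resolution. The power statement in section 9.2 concerns the primary comparison and does not enter here.

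**Assumed inputs (none is in the documents).** Median time to lasting resolution is 10 days in control, exponential, so the hazard is ln 2 / 10 = 0.0693 per day. With a true hazard ratio of 1.5, the active hazard is 0.1040. Before lasting resolution, each day has a chance f of being an isolated good day, which adds a hazard of −ln(1 − f). Follow-up is 28 daily diaries.

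**Step 1: single-day rule, equal f in both arms.** The hazards add:

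HR ≈ (0.1040 − ln(1 − f)) / (0.0693 − ln(1 − f))

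- f = 2%: (0.1040 + 0.0202) / (0.0693 + 0.0202) = 1.39
- f = 5%: (0.1040 + 0.0513) / (0.0693 + 0.0513) = 1.29
- f = 10%: (0.1040 + 0.1054) / (0.0693 + 0.1054) = 1.20
- f = 20%: (0.1040 + 0.2231) / (0.0693 + 0.2231) = 1.12

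Simulation with 200,000 patients per scenario and Efron ties gave 1.39, 1.30, 1.20 and 1.13. With f = 0 the rules agree at 1.50.

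**Step 2: two consecutive days.** With independent days, the extra hazard is about f². At f = 5%: (0.1040 + 0.0025) / (0.0693 + 0.0025) = 1.48. At f = 10%: (0.1040 + 0.0100) / (0.0693 + 0.0100) = 1.44. Simulation gave 1.49 and 1.45, and 1.33 at f = 20%.

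With day-to-day autocorrelation of 0.5, the gain is smaller in simulation: from 1.35 (one day) to 1.40 (two days) at 5%, and from 1.27 to 1.35 at 10%.

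**Step 3: good days commoner on active drug (single-day rule).**

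- True HR 1.5, 5% control against 7.5% active: (0.1040 + 0.0780) / 0.1206 = 1.51 (simulated 1.50, no dilution).
- True HR 1.5, 5% against 10%: (0.1040 + 0.1054) / 0.1206 = 1.74 (simulated 1.73).
- No true effect, 5% against 10%: (0.0693 + 0.1054) / 0.1206 = 1.45 (simulated 1.45). Two consecutive days give (0.0693 + 0.0100) / (0.0693 + 0.0025) = 1.10 (simulated 1.10).

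**Step 4: hospitalisation.** These simulations have no isolated good days, a hazard ratio of 1.5 before hospitalisation is allowed for, and hospitalised patients assumed slower to recover. They compare two possible conventions, neither of which the plan states.

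| Admitted, control / active | Censored at admission | Kept unresolved to Day 28 |
|---|---|---|
| 10% / 10% | 1.49 | 1.39 |
| 10% / 5% | 1.52 | 1.57 |
| 10% / 3% | 1.54 | 1.65 |
| 5% / 10% | 1.47 | 1.28 |

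The handling rule changes the estimate, and the sign of the difference depends on which arm has more admissions. Keeping every admitted patient unresolved to Day 28 is an extreme convention because it ignores recovery after discharge. It is not the rule recommended below.

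**The case against.** **A reader might infer that the hazard ratio is necessarily pulled toward 1.** The documents do not support that. Dilution needs a real benefit and similar fluctuation in both arms; step 3 shows no dilution, or inflation, when fluctuation differs. With no effect and equal fluctuation, the ratio stays near 1.

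**A reader might also infer that the plan censors hospitalised or dead patients.** It does not say so. It is silent, and only the general imputation rule applies. Nor does it say that the diary stops on admission. Step 4 shows that the direction can reverse: at equal 10% admission, keeping patients unresolved gives the lower ratio.

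Other fair points:

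- A PCR result and a symptom diary may reasonably carry different durability rules, so the contrast with shedding is not in itself a contradiction.
- A good day requires all symptoms, including taste and smell, to be mild or absent together. Isolated good days could therefore be rarer than assumed.
- Two consecutive days do not exclude relapse on the third, and the benefit shrinks when days are correlated.
- Clinical worsening, mortality and hospitalisation are analysed separately, so the worst outcomes are not lost from the trial.
- Section 9 defers full details, including missing data, to a SAP still to be completed.

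These points limit the claimed direction and size. They do not remove the one-entry event, the missing relapse rule, or the imputation rule that as written reaches diary days after death.

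**Conclusion.** The concern holds as a defect in the endpoint definition and in the handling of hospitalisation and death. One diary entry is enough for resolution, return of symptoms has no consequence, and missing-at-random imputation could assign a recovery after death.

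The consequence is possible distortion in either direction. The clearest case is dilution of an assumed ratio of 1.5 to about 1.30, at a 5% daily chance of an isolated good day equal in both arms. The opposite case is a spurious 1.45 with no effect, at 5% against 10%. In these two cases, with independent days, a two-day rule brings the ratios to 1.49 and 1.10. With autocorrelation of 0.5, the equal-arm comparison is 1.35 against 1.40.

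All of this rests on assumed recovery, fluctuation and admission rates, so the figures illustrate sensitivity and do not predict the bias in this trial. Only a secondary endpoint and its respiratory repeat are affected. The primary AUC conclusion is unchanged.

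**What to change.** Before unblinding, amend synopsis endpoint 8, section 9.9 and the SAP as follows:

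1. Do not impute diary data after death. Count a subject who dies before resolution as unresolved to Day 28.
2. Count a hospitalised subject as unresolved while in hospital and until post-discharge diaries meet the definition. Do not censor at admission or impute those days under missing at random.
3. Define resolution as two consecutive diary days with every COSS symptom none or mild, dated to the first of the two. Report the single-day rule and a no-later-relapse rule as sensitivity analyses.
4. Apply the same rules to the respiratory-symptom analysis, and state how a missed diary between two good days is treated.
5. Reconcile the diary frequency. The synopsis and section 8.1 make it daily, while the section 14 schedule lists self-assessment on Days 1-10, 14, 21 and 28 (the table may be condensed). If the schedule governs, consecutive days cannot be observed after Day 10.

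The cost is a few sentences, with no new data if the diary is daily to Day 28. The downside is that a resolution beginning on the last diary day cannot be confirmed.
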